### Evaluation

- We will evaluate the training by using the first three levels of the Kirkpatrick model of educational evaluation: learner satisfaction, learning outcomes and performance improvement (Kirkpatrick 1994), adapting the questionnaire we used in previous evaluation of mental health training for OH nurses (Madan et al. 2013).
- 2) We will monitor the integrity of case-management delivery through the trial by content analysing a random 40% of consultations undertaken by the case-managers. We will record if and when case-management skill/adherence drops below a pre-determined level. This will allow us to assess how much top-up training and on-going supervision case-managers are likely to require in a full trial.

# 6.3 Recruitment and sampling:

Before recruitment commences, we will train the centres on how we wish to collect sickness absence data from ESR. We will assist participating OH departments to liaise with their HR departments to ensure that the HR departments accurately record fit notes reporting CMHD onto S10 of the ESR system.

In the study centres where participants receive either the intervention or usual care, two OH nurses will recruit participants at each centre. Up to two OH nurses will be trained in case management and will deliver the intervention and the other will deliver care as usual for that trust. The duration of recruitment will be 6 months. Where possible, all staff who go on sick leave with CMHD during the 6 month recruitment period will be referred to the OH department as soon as their line manager receives a fit note. We will provide sites with wording to further raise the profile of OH and their local site's involvement in the study. The decision on whether to circulate this correspondence will be left to participating sites. The study will also recruit from those who self-refer to Occupation Health departments. All staff who go off sick with CMHD and who are referred to the participating OH departments will be provided with information about the study and invited to participate. Those who wish to participate will be asked to consent and will be screened for eligibility for the study. At the discretion of the participating study centres, participants in the intervention group will continue to receive the

intervention until they RTW or leave their employment, even if they are still on sick leave after the study has finished.

At one study centre (Guy's and St Thomas' NHS Foundation Trust; GSTT) we would like to promote the role of occupational health service in manging workers who are on sick leave due to common mental health conditions. We would like to add a brief message about the role of OH and about the Ways Back to Work study to the Workforce Directorate brief which is correspondence disseminated across the GSTT trust only targeting line managers.

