### **Outcomes:**

**Feasibility:** Rates of uptake among those eligible to participate; the frequency and nature of protocol violations; completeness of data collection; average consultation times compared to normal and mean number of follow-ups per case; extra line manager and human resource time per consultation compared to normal. Fidelity of the case-manager training.

**Acceptability:** A summary of qualitative findings representing views on the intervention and its assessment expressed by participants, case-managers, HR and line-managers. Reasons for not completing the intervention and any adverse effects.

**Measurements of costs:** Costs of delivering the package of interventions including OH nurse time, participant and manager time and cost of training OH nurses in case management.

**Manual development:** Complete specification of the intervention and standard operating procedures for different settings. A manual for training the case-managers.

**Sample size:** With a sample size of 60 we will be able to estimate a participation rate of 80% to within a 95% confidence interval of +/- 10%. We have allowed for 77 participants, so we are confident that we will have a good precision around the participation, and completion rates.

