# **WB2W Study: STUDY FLOWCHART**

# Intervention arm

# Care as usual arm

ACTIVITY (does not apply to employees who self-refer): Line manager receives fit note & refers to OH if worker agrees. Where possible, line manager gives participant information sheet (PIS) to employee. The PIS may also be sent directly to prospective participants from the occupational health team once the referral to OH ETURN TO WORK has been made. Ideally line manager immediately phones case manager to make the referral for OH follow-up otherwise the referral is made by email on the same day. (Sites will be requested to disseminate specific wording locally aimed at raising the profile of OH and their involvement in the study) ACTIVITY (Where possible, PHONE CALL from OH to worker within 3 working days of OH referral): Confirms eligibility and sends PIS if not already received OH worker books 1st app. Participant receives baseline questionnaire by post and/or email manager Sites will have the option of sending a participant

Participant receives care as usual (non-participant questionnaire sent to those who do not wish to participant in the study

Does not wish to

take part in the

study

Not eligible or

does not want to

take part

Sites will have the option of sending a participant information sheet along with appointment details to all new referrals who are booked into see a local field workers. This will provide an opportunity for field workers to screen and recruit participants who are assessed as meeting the inclusion criteria during the 1st appointment

0m questionnaire

Participant receives care as usual

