We will collect the same data on all participants and participating centres. Data from all groups will be used to answer questions about rates of recruitment and follow-up, and the acceptability and performance of methods to assess possible outcome measures. Data from Group A and Group D will provide information about the acceptability and costs of the intervention, and rates of adherence to the intervention. Data from Groups B and C will provide information about the distribution of possible outcome measures in the absence of the intervention (which would help in power calculations for a subsequent trial). Comparison of the management of participants in Groups B and C will give an indication of potential for major "contamination". The follow-up period will be six months from recruitment. Outcomes will be assessed using a mix of qualitative and quantitative methods.

Target population: NHS staff who have recently commenced sick leave because of CMHD

**Inclusion criteria:** Staff with CMHD with or without an associated physical disorder who have been off sick for a period of more than 7 days (i.e. on receipt of fit note) and less than 90

days. Staff will be screened for eligibility for entry into the study either at the time of referral to OH or during their 1st OH appointment.

**Exclusion criteria:** Staff with a psychotic disorder, bipolar disorder, substance abuse or dementia. Staff under formal investigation for misconduct or in the formal process of disciplinary action (as this may be an effect modifier).

Six OH departments have been chosen from those confirming that they wished to participate in the feasibility study in response to the questionnaire sent to the current SCIN study centres plus one ambulance trust. We have selected NHS OH departments representative of the range of NHS Trusts in the UK, providing OH services to a mixture of acute, mental health and ambulance trusts. All trusts included have electronic OH data capture systems, do not currently have early (<8 day) intervention for sickness absence or case-management in use and employ more than two OH nurses who advise on RTW in workers with CMHD.

We have allocated the participating trusts to care as usual or mixed intervention/ care as usual centres / intervention centre based on sampling groups with the aim of achieving broad comparability between the types of trust.

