# 6.5.1 Quantitative

Rates of recruitment will be calculated from the numbers of eligible participants and of those who agree to participate in the study. Characteristics of eligible participants will be recorded at baseline and will be summarised through means, medians, standard deviations, and interquartile ranges (IQRs). Characteristics will be compared between those who agree to participate in the feasibility study and those who do not. Outcome variables, including anxiety/depression score, health related quality of life score, use of antidepressants, will be summarised separately for baseline and follow-up using means and standard deviations if they are normally distributed, or through medians and IQRs otherwise. Number of days before returning to normal working hours will be summarised by medians and IQRs. For each possible outcome measure, the prevalence of missing data will be quantified. We will calculate the proportion of participants who complete the intervention, and the proportion of completed data sets.

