### 6.6 Sample size

We calculated that with a sample size of 60 we will be able to estimate a participation rate of 80% to within a 95% confidence interval of +/- 10%. We have allowed for a maximum of 77 participants so we are confident that we will have a good precision around the participation, and completion rates. All the OH departments who have confirmed that they wish to take part would expect to see more than 20 workers who go on sick leave with CMHD in a six-month period. Therefore, we consider that it is feasible to recruit 14 participants at care as usual and mixed intervention/care as usual centre and 7 participants at the intervention only centre.

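### Section 6.3 places the eligibility screen after willingness and consent, in conflict with section 6.1 and the flowchart, so the participation rate that sizes the study has no single denominator

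*Protocol*

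**What the plan says.** Section 6.3 informs and invites all staff who are off sick with a common mental health disorder and referred to a participating OH department. It then continues: "Those who wish to participate will be asked to consent and will be screened for eligibility for the study".

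Three other places fix the point of screening differently:

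- Section 6.1, inclusion criteria: "Staff will be screened for eligibility for entry into the study either at the time of referral to OH", or else at the first OH appointment. Willingness is not a condition.
- Study flowchart, OH telephone call after referral: "Confirms eligibility and sends PIS if not already received". The call is made where possible.
- Study flowchart, optional route: field workers may screen and recruit at the first appointment. OH confirms eligibility at that appointment in any case, when consent is taken.

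The quantity at stake is defined in section 6.5.1: "Rates of recruitment will be calculated from the numbers of eligible participants and of those who agree to participate in the study". The summary lists the same quantity first among the feasibility outcomes: "Rates of uptake among those eligible to participate". Section 6.6 rests the sample size on it: "with a sample size of 60 we will be able to estimate a participation rate of 80% to within a 95% confidence interval of +/- 10" percent. The same section adds: "We have allowed for a maximum of 77 participants".

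**The concern.** A rate of agreement among eligible people needs eligible decliners in its denominator. The order in 6.3 (invite, wish to take part, consent and screen) produces an eligibility decision only for people who already want to join. The order in 6.1 and in the flowchart's telephone call can produce one for everybody referred. Six sites working from one protocol could reasonably follow either order, and their denominators would then not mean the same thing.

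This matters because the participation rate is the only quantity on which the sample size is justified, and question 7 in section 4.1 asks what recruitment a future trial could expect. An error from the denominator does not shrink as more people are recruited. Eligibility not recorded at referral may also be hard to recover later for someone who declined.

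**Working it through.** **1. The plan's own figure.** Inputs from section 6.6: rate p = 0.80, half-width 0.10, 95% confidence. With the normal approximation,

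n = 1.96² × 0.80 × 0.20 / 0.10² = 61.5, so 62.

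The stated 60 is close. The half-width at n = 60 is 1.96 × √(0.16/60) = 10.1 points. The figure reproduces to rounding.

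This n counts eligible people invited, not participants. At 80%, 60 eligible people give 48 participants, and 77 participants imply 77/0.80 = 96 eligible people, with a half-width of 8.0 points. Sampling precision is therefore adequate; the weakness is in what is counted.

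**2. What each order of steps yields for a decliner.**

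| Place in protocol | When eligibility is decided | Is a decliner's eligibility known? |
|---|---|---|
| 6.3 | After wish to take part, with consent | No, read literally |
| 6.1 | At referral or first appointment | Yes if at referral; otherwise only if the person attends |
| Flowchart, telephone call | After referral, where possible | Yes if the call is made and the result kept |
| Flowchart, optional route | At first appointment | Only if the person attends and is screened before declining |

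One flowchart exit puts people who are not eligible and people who do not want to take part under a single label. The rate has to keep those two groups apart.

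**3. Size, on assumed inputs.** The protocol gives no number of decliners. Section 6.6 expects more than 20 eligible-type absences per department in six months, so 6 × 20 = 120 serves as a round number of referrals. Assume 80% are eligible, 80% are willing, and the two are independent.

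- Eligible: 120 × 0.80 = 96
- Eligible and willing: 96 × 0.80 = 76.8
- Decliners of any eligibility: 120 × 0.20 = 24, of whom 19.2 are eligible
- True rate: 76.8/96 = 80%
- All decliners counted as eligible: 76.8/(76.8 + 24) = 76%
- Only screened people counted: 76.8/76.8 = 100%

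**4. Range over the assumed number of unscreened decliners.** With 77 participants, D unscreened decliners and a share q of them eligible, the rate is 77/(77 + qD).

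| D | q = 1 | q = 0.75 | q = 0.5 | none counted |
|---|---|---|---|---|
| 19 | 80.2% | 84.4% | 89.0% | 100% |
| 25 | 75.5% | 80.4% | 86.0% | 100% |
| 30 | 72.0% | 77.4% | 83.7% | 100% |

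The distance between the extremes is 20 to 28 points. The planned interval is about 20 points wide in full.

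**5. Range over the assumed eligible share e, with 80% willing and all decliners counted as eligible.** The reported rate is 0.8e/(0.8e + 0.2).

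- e = 0.9: 0.72/0.92 = 78.3%
- e = 0.8: 0.64/0.84 = 76.2%
- e = 0.6: 0.48/0.68 = 70.6%
- e = 0.5: 0.40/0.60 = 66.7%

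In this direction the error stays within 10 points unless fewer than about six in ten referrals are eligible.

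**The case against.** A reader might infer from 6.3 that eligible decliners are never identified and that the rate cannot be calculated. The documents do not support that. Section 6.1 screens staff without reference to willingness. The flowchart confirms eligibility by telephone, provides an exit for those who do not wish to take part, and sends them a non-participant questionnaire. Section 6.4.1 collects reasons for non-participation and baseline characteristics of the eligible, and section 6.5.1 compares those who agree with those who do not. The sentence in 6.3 may describe only the confirmation of eligibility at the first appointment for people about to enter. Those invited are also already known to be off sick with a relevant disorder, so part of eligibility is settled. All of this stands, and it rules out the absolute reading.

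It does not remove the conflict. The telephone call is made only where possible, sites may choose to screen at the first appointment, and nothing says that recipients of the non-participant questionnaire were first found eligible. Section 1.0 also requires the employee to be off sick when completing the baseline questionnaire, which cannot be checked for someone who declines before that.

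It is also fair to say that 100% is the extreme case: leaving decliners out altogether departs from the definition in 6.5.1. The milder error, 76% against 80%, lies inside the planned margin. The flowchart was read by program from a figure, so the order of its boxes is uncertain, although its wording is explicit.

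A reader might also infer that recruitment differences between groups will be hidden, because section 6.1 says "Data from all groups will be used to answer questions about rates of recruitment and follow-up". That sentence does not exclude reporting by group or site, and such a breakdown may sit in an analysis plan that is not at hand. Nor is promotion confined to one usual-care site: section 6.3 offers wording to all sites, and only the directorate brief is specific to one.

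**Conclusion.** The concern holds as an unreconciled contradiction about when eligibility is decided. Where a site follows 6.3, the participation rate is biased or only bounded. Where it follows 6.1 at referral, or the flowchart's telephone call, the rate can be obtained as defined.

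In the illustration a true 80% is reported as anything from 76% to 100%. With 19 to 30 unscreened decliners beside 77 participants, the lower bound runs from 80.2% down to 72.0% and the upper bound is 100%. These figures rest on assumed numbers of referrals, eligible share and willingness, and on independence of the last two. How many sites would follow 6.3 literally is unknown. The sample size calculation is not affected.

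**What to change.** Reword 6.3 so that every referral and self-referral is screened for eligibility before, or regardless of, any expression of willingness, in line with 6.1 and the flowchart's telephone call. Keep an anonymised log at each site that records each person as eligible, ineligible or not assessed, and as agreed or declined. Split the flowchart exit that joins the ineligible and the unwilling. State how the requirement to be off sick at the baseline questionnaire is treated for someone who declines before completing it. Define participation as consented over eligible, calculated from the log, and report the number not assessed so that bounds can be given if any remain.

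The cost is a few sentences of protocol text and a small amount of logging at six sites. The sample size stays as it is. Reporting the rate by group and site as well as overall is sensible but secondary. Counting recorded S10 absence spells from the electronic staff record as an upstream denominator is optional: section 6.3 indicates that centres need help to record that code accurately, and the code also covers other psychiatric illness.

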# 6.4 Data collection and follow up 6.4.1 Quantitative data

Data on sickness absence for CMHD will be collected for six months after the participant enters the study from S10 on the participating centre's ESR and by self-report questionnaire. Study participants will be given a self-administered baseline questionnaire to complete at the time of entry to the study (t=0). They will be sent a follow-up self-administered intermediate questionnaire at three months (T=3) and a final follow-up self-administered questionnaire at six months (t=6) after entry to the study. Note, all participants will complete the same baseline and intermediate questionnaires. Responses provided in the intermediate questionnaire will than determine which version of the final questionnaire will be administered i.e. final questionnaire (version 1) will be administered to those employees who are back at work in any capacity for more than four weeks at the three month time point (T=3); final questionnaire (version 2) will be administered to those who are still off on sick leave at T=3months due to their mental health condition (including those who have not returned to sustained work) or those who did not return the intermediate questionnaire.

Participants will be invited to complete paper-based questionnaires. This will be returned to the central research team using business reply envelopes. A series of reminders will be used to encourage return of the study questionnaires for non-responders. The reminders will include, one email reminder, one telephone reminder and finally a replacement questionnaire will be sent to the participants preferred postal address. To allow to send participants 3 and 6 months questionnaires (and reminders if needed), we will collect contact details from participants (name, surname, mobile phone, email address, home postal address). Contact details will be collected together with the baseline questionnaire.

We will collect information about: rates of recruitment; reasons for non-participation; baseline characteristics of those eligible for inclusion; adherence to the intervention in those allocated to receive it and the management of those who are not; and rates of successful follow-up. Additionally, we will collect data on the distribution of possible outcome measures, including, reduction in anxiety/ depression, health-related quality of life, change in antidepressant use and RTW during the six month study period. Full and partial return to work will be measured by total days of sickness absence before return to work and self-reported number of hours worked. We will collect information about participants' referral to and uptake of improving access to psychological therapies (IAPT) services and the Government's Fit for Work Service We will record any protocol violations, reasons for not completing the intervention and any adverse events.

At the sponsor site (Guy's and St Thomas NHS Foundation), we will conduct further exploratory work to better understand the factors impacting on the identification and referral of employees who are on sick leave with a common mental health disorder. Where appropriate and with relevant permissions, this may include reviewing information on existing management referrals. These insights will be pooled with information obtained from the focus group interviews.

Costs of delivering the package of interventions including OH nurse time, participant and manager time and cost of training OH nurses in case management.

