### 2.4 Proposed data collection tools

In the feasibility study, we will test the acceptability and feasibility of data collection tools that are proposed for use in a full trial and at the same time generate information that can be used to refine the design of the full trial. The measures of interest include clinical and occupational outcomes, prognostic and cost-effectiveness indicators. The data will be obtained largely through self–completed questionnaires and from electronic data collected by ESR at each participating centre. ESR is in use across all NHS Trusts and Health Boards and has a specific code (code S10) for sickness absence due to anxiety/ stress/ depression and mental health.

There is no consensus on what the best tools for collecting data on relevant occupational outcomes are. Indeed, recently published NICE Guidelines (National Institute for Health and Care Excellence 2015) specifically called for more research on how the effectiveness of workplace health policies and programmes can be measured. We have chosen tools that have been used successfully in other studies, and we consider will be feasible to use in this study.

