# 2.4.2 Occupational outcomes

We will measure full RTW (defined for this study as working the same days or hours per week as before sickness absence in an identical or equivalent role for at least four weeks) and partial RTW (defined as working any number of hours in any role) through the ESR and self-completion questionnaires. A study examining a multi-stakeholder perspective on the definition of RTW after sickness absence due to CMHD found that definitions of RTW based on working days and hours may not accurately reflect the priorities of all stakeholders (Hees et al. 2012). Therefore we will select the most appropriate questions and discuss with our public and patient involvement (PPI) representatives.

A number of instruments have been developed to measure presenteeism, and whilst all have pros and cons we will measure workability by using the Work Ability Index (Ilmarinen, Tuomi 1992). This self-report questionnaire has been used in other sickness absence studies and will allow us to explore the effect of physical co-morbidity on work ability (Ahlstrom et al. 2010) and has shown to be a reliable instrument in this context. We will also use the Work and Social Adjustment Scale (Mundt et al. 2002) as a measure of global functioning. Using both these measures of occupational outcomes will allow us to compare the results from the measures and select which one would be the optimum measure in the full trial.

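### ESR absence is extracted only under code S10, so within that source an absence continuing under another code, or a participant leaving employment, can look like a return to work

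*Protocol*

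**What the plan says.** Section 6.4.1 of the protocol states that data on absence for CMHD "will be collected for six months after the participant enters the study from S10 on the participating" centre's record system. The same sentence adds a second source: "ESR and by self-report questionnaire". S10 is the only ESR code named for follow-up. Section 2.4 explains its scope: ESR "has a specific code (code S10) for sickness absence due to anxiety/ stress/ depression and mental health".

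The outcome that these data feed is not tied to a cause. Section 2.4.2 gives this definition of a full return: "working the same days or hours per week as before sickness absence in an identical or equivalent role for at least four weeks". Any hours worked, in whatever role, count as a partial return. Both are to be measured "through the ESR and self-completion questionnaires", with no code named at that point. Section 6.4.1 later says that full and partial RTW "will be measured by total days of sickness absence before return to work and self-reported number of hours worked", again without restriction by cause.

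The inclusion criteria in section 6.1 admit "Staff with CMHD with or without an associated physical disorder". Section 6.3 commits the team to helping HR departments code CMHD fit notes to S10, and it names leaving employment as one point at which the intervention stops.

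**The concern.** The record source is specific to a cause, and the outcome is not. When S10 days stop, three things may have happened: the person is back at work, the person is still off under a fit note that gives another reason, or the person has left. The extract as specified cannot separate them. The protocol itself makes the second and third possible, since physical comorbidity is allowed and leaving is foreseen.

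The error runs one way. Within the ESR component, both routes make return look earlier or more frequent than it was.

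This study tests no treatment effect, so the stake is the quality of what it hands on. Section 2.4 says that data collection tools proposed for the full trial are being tested, and section 4.2 promises a report on the best ones. Section 6.1 uses Groups B and C to describe outcomes without the intervention, for later power calculations. An S10-only extract cannot show whether S10 is good enough for that purpose.

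**Working it through.** **Plan's own figure.** The protocol gives no rate of re-coding or leaving, so there is no figure on this point to reproduce. Its one precision statement (section 6.6: 60 people, 80%, within 10 points) concerns participation. It reproduces to rounding, 1.96 × √(0.8 × 0.2 / 60) = 0.101, and has no bearing here.

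**Step 1: what each source can show.**

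| Situation at a given date | S10-only ESR | All-code ESR with end date | Self-report, if returned |
|---|---|---|---|
| Working | no absence | no absence | hours worked |
| Off, fit note reports a CMHD | absence | absence | not working |
| Off, later fit note without a CMHD | no absence | absence, other code | not working |
| Left employment | no absence | end date | not working in the trust |

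In the S10-only column, rows one, three and four are the same. That is the defect. An SAP could set rules for classifying such people, but it cannot recover episodes or end dates that were never extracted.

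**Step 2: who is exposed.** A participant who returns the questionnaires supplies hours worked, which can correct a misleading S10 record. A participant who does not return them has only the S10 record. If ESR and self-report disagree, S10 data alone cannot say whether the cause is re-coding, leaving or faulty recall. The routing of the six-month questionnaire adds a small ambiguity: a person off at three months for a physical reason is not clearly assigned to either version.

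**Step 3: size, by assumption.** Inputs: N = 77 (section 6.6) and 49 care-as-usual participants (21 + 28, section 6.1). Assumed: true return at six months t = 0.75, a share m of non-returners whose S10 spell ends through re-coding or leaving, and S10 read alone as RTW. The 75% is only loosely anchored. Section 2.1 reports that over 75% eventually return, with no six-month figure.

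- Apparent return = t + (1 − t) × m
- False returns = N × (1 − t) × m

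| m | Apparent return | False returns of 77 | False returns of 49 |
|---|---|---|---|
| 10% | 0.75 + 0.25 × 0.10 = 77.5% | 1.9 | 1.2 |
| 25% | 0.75 + 0.25 × 0.25 = 81.3% | 4.8 | 3.1 |
| 50% | 0.75 + 0.25 × 0.50 = 87.5% | 9.6 | 6.1 |

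These are upper figures for a given m, because self-report would correct some of the cases. They also leave out one effect: someone re-coded who then returns within six months is not a false six-month return, but that person's S10 days still understate the time to return.

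**The case against.** The strongest reply is that absence data come from two sources by design. The sentence that names S10 goes on to self-report, the version 1.3 entry in the version tracker shows that this was deliberate, and self-reported hours are collected as well. RTW is defined by working. This stands, and it confines the problem to the ESR component.

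Several stronger readings are tempting, and the protocol does not support them:

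- A reader might infer that the end of an S10 record counts as RTW. Nothing in the protocol says so.
- A reader might infer that ESR is the designated fallback for missing questionnaires. It is given no such role. The stated response to non-return is an email, a telephone call and a replacement form, with a final questionnaire version that covers those who missed month three. ESR would simply be the only source left for people who still do not reply.
- A reader might infer that a fit note naming both a physical disorder and a CMHD would be missed from the start. Section 6.3 aims to have notes that report a CMHD coded to S10. The remaining gap is a later note that drops the CMHD.
- A reader might count the lack of a leaver or competing-event rule as an error. Such rules commonly sit in an SAP, which is not shown.
- A reader might apply a 10% re-coding rate to all 77 people, get about 8 false returns, and set them against 19 non-returners (0.25 × 77), so that non-return falls to (19 − 8)/77 = 14%. That assumes that 8/19 = 42% of non-returners are re-coded or leave, which is towards the high end of the range above.

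It can also be said that RTW is one of several candidate outcomes in a descriptive study, and that Phase 2 reviews the findings before any trial is designed. That limits the consequence. It does not remove it, because the Phase 2 review would have no data on absences outside S10.

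**Conclusion.** The point holds for the ESR component. Section 6.4.1 names a mental-health code as the only record source for follow-up absence, while RTW in sections 2.4.2 and 6.4.1 means working, regardless of cause. Within that source, a continuing absence under another code, or departure from the trust, can look like a return. Self-report limits this, so the exposure lies mainly with questionnaire non-responders and with any comparison of the two sources.

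The size is unknown. Under the stated assumptions it runs from about 2 to 10 people in 77, or 2.5 to 12.5 percentage points of apparent return, always towards return. It does not threaten the feasibility aims on recruitment and acceptability. It weakens the evidence on one data source that the study sets out to test, and it may weaken inputs to a later power calculation. This is a cheap improvement, not a fatal flaw.

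**What to change.** Amend section 6.4.1 so that, for each participant over the six months, the ESR extract covers every sickness-absence episode (start, end, reason code) and the employment end date where there is one. Derive ESR-based RTW from all-cause absence and reconcile it with self-reported absence and hours. Report S10-only days alongside, with the proportion of spells that change code. That proportion would itself tell the team whether S10 alone would serve in a full trial.

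The cost is a wider query at six trusts, with no extra visits for participants. The real downside is that the extract brings in absence reasons unrelated to CMHD. The information sheet and consent wording are not among the pages available, so they must be checked, and amended if they do not cover this, before the query is widened.
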